7.5. Safety Analysis

Adverse events and SAEs will be reported in terms of the number of participants with at least one event per arm and using descriptive statistics, as unadjusted patient proportions within and between arms with 95% confidence intervals using exact methods where appropriate, such as the Wilson method (26) (with none versus with at least one event). Numerators and denominators will be presented. For the most prominent gastrointestinal disorders (in at least 10% of participants in either treatment group), as well as AEs that lead to treatment discontinuation, details of the overall number of events, timing to reporting of first such event by participant (median (IQR) time since randomisation), severity, and duration will be described as per preferred term. Denominators will generally be participants over the trial period, although between-visit stratification will be considered, as will a person-years denominator depending on the variability in follow-up. *P*-values will not be used taking account of guidance given in the CONSORT statement extension for harms (27, 28). Volcano (space-saving graphical summary) or dot plots may also be presented if frequent adverse events occur(29).

Objective	Variable	Main summary statistic	Statistical method for comparison between arms and inference type
7 To determine compliance during the 12-month intervention	Firstly, by accountability of returned used sachets. Secondly, communicated verbally by the participant (such during COVID periods where visits were done remotely)	Proportions of 50% to 95% compliance (in steps of 5%)	Difference in proportions with 95% CIs Comparison of compliance distributions
	Percentage compliance for a subject will then be defined as number of used sachets divided by the total number of sachets expected to have been taken over the 12-month study period)*100%.† In periods where the sachets have not been returned it will be assumed that the compliance was the same as in the average of the other periods (0- 2months, 2 -6 months, 6 -12months). For participants reporting treatment discontinuation or that were lost to follow-up, we will consider zero used sachets from these timepoints onwards. Those with no treatment compliance data will be regarded as below 50% compliance for purpose of analysis.	Medians (IQR)	Difference in medians

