4.6. Schedule of Time and Events

A full schedule on the timing of measures is provided in below (as in section 6.5 of protocol). The plus or minus sign are a target/guide for when the visits should happen. If any fall below/above these, the closest measurement to the visit will be used.

Assessment	Screening	Baseline/ Randomisation (1-4 weeks after screening)	2 months (+/- 2 week)	6 months (+/- 4 weeks)	12 months (+/- 4 weeks)
Consent	X				
Demographics	X				
Randomisation		Х			
Medical History	X	Х	X	Х	Х
Concomitant medications	X	Х	Х	Х	Х
Pregnancy test - females only	X	Х	X	Х	Х
Electrocardiogram (ECG)	X				
Vital signs: DBP, SBP and HR	X	X	X	Х	Х
Trial intervention		Х	X	Х	
Height, body weight, waist/hip measurements, BMI, body composition	X	Х	Х	Х	Х
Fasting blood test (glucose, insulin, lipid profile)		Х		Х	Х
Full Blood Count & Vitamin B12	X				
Food diary		Х	X	Х	Х
IPAQ	X	Х	X	X	Х
Lifestyle questions	X	X	X	X	X
Sachet count (compliance)			X	X	X
Adverse event tracking		X	X	X	X

Mechanistic evaluation

(52 ppts; Imperial site only)

(c= ppis, imperial site only)			n	•	i
Assessment	Scree ning	Baseline/Randomisation (1-4 weeks after screening)	2 months (+/- 2 week)	6 months (+/- 4 weeks)	12 months (+/- 4 weeks)
Energy expenditure (indirect calorimetry)		Х			Х
Appetite regulation (VAS, food diary, ad libitum test meal, and blood tests for anorectic gut hormones)		Х			Х
Substrate oxidation/DNL (via stable isotype tracers in water consumption) – ¹³ C breath, urine and blood samples		Х			Х
Gut microbiota (stool sample and hydrogen breath test)		Х			Х
Neuroendocrine cell number (stool sample)		X			X
Accelerometry		Х			Х

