6.4. Safety Variables

Adverse events will be classified by "type" (serious/non-serious), severity (mild, moderate, severe), causality/relationship to study treatment (unrelated, unlikely, possibly, probably, definitely), expectedness (expected vs unexpected, SAEs only), outcome (resolved, resolved with sequelae, persisting, worsened, fatal) and MedDRA Structure (system organ class (SOC), high level group term (HLGT), preferred term (PT), lowest level term (LLT)).

According to the safety reporting manual of iPREVENT the causality is made by the investigator responsible for the care of the participant and the expected adverse events of the trial are gastrointestinal symptoms. All important abnormal laboratory test results occurring during the trial will be recorded as adverse events. Pregnancies at any point during the trial will also be recorded.

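### Section 7.5 times gastrointestinal events to when they were reported, so the planned median (IQR) can follow the visit calendar instead of onset.

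*SAP*

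**What the plan says.** SAP section 7.5 adds detail for two groups of events: "For the most prominent gastrointestinal disorders (in at least 10% of participants in either treatment group), as well as AEs that lead to treatment discontinuation". For these it plans that "timing to reporting of first such event by participant (median (IQR) time since randomisation), severity, and duration will be described as per preferred term". Reporting is not defined. It could mean the day the site was told, the day of data entry or, loosely, the day the event began.

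The schedule in section 4.6 has a row for "Adverse event tracking", marked at baseline/randomisation, 2 months (± 2 weeks), 6 months (± 4 weeks) and 12 months (± 4 weeks). It lists no scheduled adverse event contact between these visits. The windows themselves are loose: "The plus or minus sign are a target/guide for when the visits should happen".

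The other safety summaries in section 7.5 do not use this clock. The main one is that "Adverse events and SAEs will be reported in terms of the number of participants with at least one event per arm". Visit intervals appear once, for denominators, and only as a possibility: "although between-visit stratification will be considered".

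**The concern.** The safety profile of IPE is the first secondary objective (section 3.5). Section 6.4 says that "the expected adverse events of the trial are gastrointestinal symptoms", and section 2.4 motivates IPE partly by the gastrointestinal side effects of dietary fibre. Whether symptoms begin in the first days or build up over months, and whether the arms differ in this, is what a time-to-first-event summary is meant to show. It is the only onset-type statistic that the SAP plans.

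A report date answers a different question. The gaps between scheduled contacts are about 2, 4 and 6 months. An event that begins in week 1 and is raised at the next visit is timed at about 2 months, and one that begins in month 7 at about 12 months. Two arms with clearly different onset could then show the same median.

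**Working it through.** The SAP states no figure for this item, so there is none to reproduce. The check asks how the planned statistic behaves under its own visit schedule.

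**Inputs from the SAP.** Visits at 2, 6 and 12 months with their windows (section 4.6); median and IQR of time from randomisation to reporting (section 7.5).

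**Assumptions.** Time to first event is exponential with median *m* months, restricted to events before 12 months. A share *s* of events is reported at onset and the rest at the next visit. The SAP gives neither *m* nor *s*, so both are varied.

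**Step 1: all reporting at visits (*s* = 0).** Let F(t) be the proportion of first events that start before *t*:

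F(t) = (1 − 2^(−t/m)) / (1 − 2^(−12/m))

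The reported median is 2 months whenever F(2) exceeds one half, that is, whenever the true median onset is below 2 months. This does not depend on the exponential form.

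| *m* (months) | F(2) | True median onset, events before 12 months | Reported median |
|---|---|---|---|
| 0.1 | 1.00 | 0.1 | 2 |
| 0.5 | 0.94 | 0.5 | 2 |
| 1 | 0.75 | 1.0 | 2 |
| 1.5 | 0.61 | 1.5 | 2 |
| 3 | 0.39 | 2.7 | 6 |
| 5 | 0.30 | 3.8 | 6 |

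For *m* = 0.1 and 0.5 the IQR also collapses, to 2–2 months.

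**Step 2: the same in days.** Place the visits at days 61, 183 and 365. With an exponential mean of 10 days, the true median is 10 × ln 2 = 7 days and the IQR is 10 × ln(4/3) to 10 × ln 4 = 3 to 14 days. With a mean of 30 days they are 21 days and 9 to 42 days. The shares starting before day 61 are 1 − exp(−61/10) = 99.8% and 1 − exp(−61/30) = 87%. Both exceed 75%, so both series give a reported median (IQR) of 61 (61–61) days. Two arms with means of 7 and 25 days have true medians of 5 and 17 days, and both also give 61.

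**Step 3: visit windows.** Moving visits at random within their windows gives reported medians of 2.0 to 2.3 months for *m* from 0.1 to 1.5. The zero-width IQR softens (for *m* = 0.5 it is 1.8 to 2.3 months), but the median hardly moves.

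**Step 4: some events reported at onset.** For true median onset below 2 months, the reported median leaves the 2-month visit only when *s* × F(2) exceeds 0.5, so *s* must exceed 0.5 / F(2):

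- *m* = 0.5: 0.5 / 0.94 = 53%
- *m* = 1: 0.5 / 0.75 = 67%
- *m* = 1.5: 0.5 / 0.61 = about 83%

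Simulation agrees:

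- *s* = 25%: medians are the same as in step 1.
- *s* = 50%: still 2 months for *m* from 0.25 to 1.5. For *m* = 0.1 the statistic sits on a knife edge (0.98 in the run), and for *m* = 3 it is 3.6.
- *s* = 75%: 0.16, 0.79, 1.6 and 3.0 months for *m* = 0.1, 0.5, 1 and 3. Different onsets can be told apart again, though the values run somewhat high, *m* = 1.5 still gives 2.0, and the upper quartile stays at 2 months for *m* up to 0.5.

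**The case against.** The strongest reply is that the effect depends on something the SAP does not state. The schedule lists visit assessments; it does not say that reports between visits are refused or left unrecorded. Section 6.4 refers to a separate safety reporting manual, and such documents commonly settle how events are captured. If most events are reported as they happen, the problem largely fades, as step 4 shows. This stands, and it is why the point is conditional.

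A second reply is that reporting may be loose wording for onset, since "severity, and duration will be described as per preferred term" and duration needs a start date. That is possible. But anyone programming from the text would take the report date, so the sentence needs correcting on either reading.

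A third is that onset dates recalled after gaps of four to six months are imprecise. This is true, but an approximate onset date is usually closer to the event than a visit date months later.

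A reader might go further and infer that the median certainly reflects the visit calendar, or that the trial will not describe tolerability. The SAP supports neither. The first needs visit-only or mostly visit-based reporting, which is not stated. The second ignores that participants with an event, event counts, severity, duration and events leading to discontinuation are all summarised without the report date.

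**Conclusion.** The point holds in a limited form. Section 7.5 names the reporting date, and section 4.6 spaces scheduled adverse event tracking widely enough for that choice to matter. With all reporting at visits, the planned median is about 2 months for any true median onset from days to about six weeks. With about 75% reported at onset, it largely follows onset. Those shares, and the exponential onset, are assumptions.

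Only one descriptive item is affected. It carries no p-value and no decision rule, and it does not touch the primary analysis. The correction is still worthwhile because it is cheap and makes the statistic answer the question that the first secondary objective raises.

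**What to change.** In section 7.5, redefine the timing item as time from randomisation to the recorded onset date of the participant's first event of that type, keeping median and IQR by preferred term. If reporting was always meant as onset, say so. Add that onset dates recalled at a visit are approximate.

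The cost is one sentence and a different date variable. No new data are needed if onset dates are held. The duration summary suggests that they are, but the SAP does not say so, and this should be confirmed first.

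A cumulative incidence display by arm is optional. If one is added, censoring at last contact assumes that dropout is unrelated to adverse events, which is doubtful for gastrointestinal intolerance. The 25% loss in sections 4.5 and 7.2.3 concerns 12-month weight data and is not an estimate of lost adverse event follow-up.

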6.7. Compliance variables

This is of interest in itself but it is also involved in the supplementary investigation as mentioned above.

Secondary objective:	Variable	Type of variable	Timepoint(s) of evaluation of endpoint
To determine compliance during the 12-month intervention	Accountability of returned used for all subjects.	Continuous	2, 6 and 12 months

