7.6. Compliance Analysis

[†]If return of sachets is low (median of used and unused <50% of those dispensed) we will check for the correlation between this objective measurement of compliance (accountability of unused sachets) and the self-reported measurement 'How many times did subject miss a sachet since the previous study visit?' and if it turns to be high (\geq 0.7), and this self-reported measurement has less missing data, than the self-reported measure will be used to assess compliance. For subjects who become pregnant, only the time up to this event will count when assessing compliance.

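### SAP 6.7 and the 7.6 table score compliance from returned used sachets, the 7.6 footnote from unused ones, and no rule says how to score sachets unaccounted for in a partly returned period

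*SAP*

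**What the plan says.** Section 6.7 gives the compliance variable as "Accountability of returned used for all subjects" (the noun is absent). The compliance table of 7.6 names two sources in order: "Firstly, by accountability of returned used sachets" and then "Secondly, communicated verbally by the participant (such during COVID periods where visits were done remotely"). It defines percentage compliance as "number of used sachets divided by the total number of sachets expected to have been taken over the 12-month study period", times 100.

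The footnote to that table refers to "this objective measurement of compliance (accountability of unused sachets").

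Three provisions deal with incomplete return:

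- **Averaging.** The rule reads "In periods where the sachets have not been returned it will be assumed that the compliance was the same as in the average of the", with the remaining visit intervals (out of months 0–2, 2–6 and 6–12) as the base of that average. The amendment table in section 9 explains that this replaced an assumed compliance of zero, on the advice of the DMC Chair/Statistician.
- **Verbal report**, the second source above.
- **Self-report switch.** "If return of sachets is low (median of used and unused <50% of those dispensed"), the count is correlated with a question on how many times a sachet was missed. If the correlation is at least 0.7 "and this self-reported measurement has less missing data, than the self-reported measure will be used to assess compliance".

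Sections 5.3.3 and 7.7.1 classify compliers at cut-offs from 50% to 95% (5.3.3 gives steps of 5%). Section 7.7.1 obtains the CACE by dividing the estimated effect by the proportion compliant.

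**The concern.** A count of used sachets and a count of unused sachets are not two names for one measure. They treat a sachet that never comes back in opposite ways, and the SAP does not say which count governs. It also gives no rule for a period in which some sachets are returned and others are not, which is likely when people must keep empty sachets for months between visits.

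If the table is followed literally, compliance partly records whether participants keep their empties, and people who took the supplement can be classed as non-compliers. If the footnote is followed, discarded and lost sachets all count as taken. Compliance is secondary objective 6 in section 3.5 and sets the CACE denominator at every cut-off, so both results depend on a choice that has not been made.

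**Working it through.** The SAP states no compliance or return figure, so there is nothing of its own to reproduce.

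**Inputs.** The formula is used/expected (7.6 table). The cut-offs are 50% to 95% in steps of 5% (5.3.3). True compliance *c* and return share *r* are assumptions. For simplicity *r* is the same for used and unused sachets, and sachets dispensed equal sachets expected.

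**Formulas for a partly returned period.**

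- Used count: *c* × *r*
- Unused count: 1 − (1 − *c*) × *r*

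**Results for *c* = 80%.**

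| *r* | Used count | Unused count |
|---|---|---|
| 50% | 0.8 × 0.5 = 40% | 1 − 0.2 × 0.5 = 90% |
| 60% | 0.8 × 0.6 = 48% | 1 − 0.2 × 0.6 = 88% |
| 80% | 0.8 × 0.8 = 64% | 1 − 0.2 × 0.8 = 84% |
| 100% | 80% | 80% |

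With *c* = *r* = 60% the scores are 36% and 76%, on opposite sides of the 50% cut-off.

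**Ceiling under the used count.** As *c* cannot exceed 1, the score cannot exceed *r*. At *r* = 60% the cut-offs from 65% to 95% cannot be reached, and passing 50% needs true compliance of 0.5/0.6 = 83.3%. At *r* = 80% the cut-offs from 85% to 95% cannot be reached, and passing 50% needs 0.5/0.8 = 62.5%.

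**Do the three provisions remove it?**

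- *Averaging* applies when a period's sachets were not returned; it is silent on partial return. Take 80% compliance in months 0–6 (182 of 365 days), with all those sachets returned. If nothing comes back for months 6–12, the score is 80%. If one used sachet comes back and averaging is therefore not applied, it is (0.8 × 182 + 1)/365 = 40%.
- *Verbal report* is listed second, with remote visits as its example. No rule says when it replaces an incomplete count made in clinic.
- *The self-report switch* needs a median return below 50%, most naturally a trial-level figure, plus the correlation and missing-data conditions. If typical return is 50% or more, it is not reached.

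**Direction of the correlation.** The self-report item counts missed sachets. It should rise with the unused count and fall with the used count. A threshold of at least 0.7, read as written, is plausible for the footnote's measure and unlikely ever to be met by the table's.

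**Effect on the CACE.** The estimate is the effect divided by the proportion compliant. For illustration, the SAP's 2 kg detectable effect with assumed proportions of 0.8, 0.6 and 0.4 gives 2.5, 3.3 and 5.0 kg. Undercounting compliers inflates the CACE; overcounting shrinks it.

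**The case against.** The word unused appears only in a contingency check, in a sentence that also mentions both used and unused sachets, so it may be a slip. The formula says used sachets, not returned used sachets, and verbal report may supply part of the count. Non-return was considered: section 7.6 was revised on this point. The CACE is described as more exploratory than the primary analysis and is spread over many cut-offs because none is established. Return procedures may also sit in the protocol, which is not at hand.

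Much of this stands, and it rules out several stronger readings:

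- A reader might infer that the inconsistency itself makes discarded sachets count as untaken. It does not. That follows from the used count alone; the unused count errs the other way.
- A reader might infer that nothing in the SAP can correct the score. Verbal report might; what is missing is the rule for when it does.
- A reader might test the 50% trigger on one participant's return share. The wording points to a median across participants, so one person's share does not decide the switch.
- A reader might put a fixed inflation factor on the CACE. Without a return rate or compliance distribution, any factor is assumed.

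What the objection does not remove is the undefined measure and the unscored partial return. The section 9 rationale points the same way: assumed zeros were judged unrealistic for unreturned periods, yet the literal count still assigns zero to each unreturned sachet in a partly returned one.

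**Conclusion.** The point holds as an inconsistency in the definition together with a missing scoring rule. At an assumed return share of 60% to 80% and true compliance of 80%, the two readings differ by 40 percentage points (88 − 48) down to 20 (84 − 64); at full return they coincide. These sizes rest on an assumed return share that is equal for used and unused sachets, and on dispensed equalling expected. The actual bias, and even its direction, is unknown until the measure is fixed and return rates are seen.

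The reach is the compliance objective and the supplementary CACE. A reader might infer that the main weight result is also in doubt; it is not, because the primary ITT model does not use compliance. The change should be made before unblinding, because the choice moves the CACE denominator.

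**What to change.** 1. Define the objective measure once and use the same wording in 6.7, the 7.6 table and the footnote. State the direction of the expected correlation with the missed-sachets item, and when verbal report replaces an incomplete count.
2. Do not score unaccounted sachets in a partly returned period as untaken by default. State one main rule that treats them as missing, in line with the averaging rule for unreturned periods.
3. Report compliance and the CACE under both bounds: returned used/expected, and (dispensed − returned unused)/expected, the latter capped at 100%.

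The cost is SAP wording and a few lines of derivation code; the low-return trigger already needs both counts.

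The downside is that any main rule rests on an assumption about return habits and may over- or understate compliance. Used/(used + unused) among returned sachets is one candidate, but it is not neutral. Suppose a participant takes 95% of 365 sachets (347 taken, 18 unused), returns all the unused and 60% of the empties (208). The ratio is 208/226 = 92%, short of the true 95%. A participant who returns one empty and nothing else would score 100% for that period. The two bounds, 208/365 = 57% and 347/365 = 95% in the first example, show how much depends on the rule.

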7.6. Compliance Analysis

[†]If return of sachets is low (median of used and unused <50% of those dispensed) we will check for the correlation between this objective measurement of compliance (accountability of unused sachets) and the self-reported measurement 'How many times did subject miss a sachet since the previous study visit?' and if it turns to be high (\geq 0.7), and this self-reported measurement has less missing data, than the self-reported measure will be used to assess compliance. For subjects who become pregnant, only the time up to this event will count when assessing compliance.

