Inulin Control	$= N_{c} - (N_{12}/N_{1})*N_{c}$	$= (N_{12}/N_1)^*N_C$	Nc
	$= (M_{C} - (N_{12}/N_{1})*M_{12})/(N_{11}/N_{1})$	= M ₁₂	Mc

(Statistics preceded by an "=" are unobserved, and are estimated from the observed statistics.) The method is adapted to a more plausible MAR assumption by replacing the sample sizes at follow-up by those at baseline. In the presence of missing compliance, it will be primarily assumed that the participant is a non-complier.

The CACE estimate will instead be obtained from the analysis LME model applying the strategies in table 7.7, as this adjusts for baseline and refers to the population for the supplementary investigation. The CACE estimate is the ratio of the estimated treatment effect to the proportion compliant, following the rule of thumb (31) (estimate LME/ proportion compliant).

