8. IMPACT OF COVID-19

8.1. On data quality and usage of data

The possibility of subjects having COVID-19 was already addressed in tables 7.2.2 and 7.7.

As written in the iPREVENT guidance document of COVID-19 restrictions, all in-person clinic study visits have been suspended until further notice, with follow up visits being conducted only remotely. This means that body weight (primary outcome) will be self-reported during the restriction time.

When subjects return to clinic study visits, these will be asked to measure their weight before going into the clinic so that the self-reported weight can be compared with the weight measured at the clinic using the Bland and Altman limits of agreement and correlations. Since the self-reported weight was collected at the pre-screening questionnaire it is possible to measure change in measured weight and self-reported weight. These will be discussed with independent committees.

Since it is hoped that all subjects reach the 12-month visit in a non-restricted/covid-19 period, only the weight measured at the clinic will be considered for the primary outcome of the trial.

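### The rule for switching to self-reported compliance checks only correlation, which cannot detect a shift in level, although compliance is used at absolute cut-offs and as the CACE denominator

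*SAP*

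**What the plan says.** The compliance table that goes with section 7.6 defines a participant's percentage compliance as the "number of used sachets divided by the total number of sachets expected to have been taken over the 12-month study period". Returned used sachets are the first source, and the participant's verbal report is the second. The summary is the proportion reaching each level from 50% to 95% in steps of 5%.

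The footnote in 7.6 adds a contingency. It applies when the median return of used and unused sachets together is below 50% of those dispensed. In that case "we will check for the correlation between this objective measurement of compliance (accountability of unused sachets) and the self-reported measurement" of how many times a sachet was missed since the previous visit. If the correlation is at least 0.7 and "this self-reported measurement has less missing data, than the self-reported measure will be used to assess compliance". All three conditions must hold.

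Section 7.7.1 then obtains the CACE as a ratio: "estimate LME/ proportion compliant". It does so at compliance thresholds from 50% to 95% and describes the analysis as more exploratory than the primary one.

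For another self-reported quantity, body weight under COVID-19 restrictions, section 8.1 plans that it "can be compared with the weight measured at the clinic using the Bland and Altman limits of agreement and correlations".

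**The concern.** Of the three conditions, low return and fewer gaps describe completeness. Only the correlation sets one measure against the other. A correlation asks whether participants are ranked in a similar, linear way. It does not change if everyone's compliance is moved up by a constant, or if everyone's misses are scaled down by the same factor.

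Every later use of compliance depends on its level: whether a participant reaches 50%, 80% or 95%, what proportion does so, and what the LME estimate is divided by. A self-report that systematically leaves out missed sachets could therefore pass the check and still move many participants across the cut-offs.

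At stake are the compliance objective (secondary objective 6 in section 3.5) and the supplementary CACE estimate. Overstating the proportion compliant pulls the CACE toward the intention-to-treat estimate.

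The correlation can also be computed only where both measures exist. When returns are poor, that is a possibly unrepresentative part of the sample.

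**Working it through.** The 0.7 threshold is a decision rule, so there is no SAP figure to reproduce. The SAP gives no compliance data, so the sizes below are illustrations under stated assumptions.

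**Step 1: the principle, without a distribution.** Let C be true percentage compliance and k the share of true misses that is reported. Recorded compliance is S = 100 - k(100 - C). With k = 0.5 for everyone, C = 50 gives S = 100 - 0.5 x 50 = 75. S is an exact increasing linear function of C, so r = 1.00 although a participant at 50% is recorded at 75%.

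**Step 2: why r does not reveal k.** Add a reporting error with SD e, and let s be the SD of C. Before truncation to 0-100, r = ks / sqrt(k²s² + e²), which depends only on ks/e. With s = 20:
- unbiased reporting, k = 1, e = 10: 20/sqrt(400 + 100) = 0.89
- half of misses reported, k = 0.5, e = 5: 10/sqrt(100 + 25) = 0.89

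The correlation is the same in both, but only the second is biased.

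**Step 3: effect on the cut-offs and the CACE.** Assumptions: C ~ 100 x Beta(3, 1.3), so the mean is 3/4.3 = 70% and the SD about 20 points. Reported misses are k(100 - C) plus normal error, truncated to 0-100. Shrinkage of the CACE is 1 - (true proportion compliant / recorded proportion compliant), because the numerator does not change. Simulated results:

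| k | error SD | r | at or above 50%: true, recorded | shrinkage | at or above 80%: true, recorded | shrinkage |
|---|---|---|---|---|---|---|
| 0.7 | 10 | 0.82 | 82%, 94% | 13% | 37%, 50% | 27% |
| 0.7 | 12 | 0.77 | 82%, 93% | 12% | 37%, 50% | 26% |
| 0.5 | 10 | 0.72 | 82%, 99% | 17% | 37%, 65% | 43% |

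All three rows pass the 0.7 check. As an example of the arithmetic, the last cell is 1 - 36.9/64.8 = 43%.

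**Step 4: in kg, for an assumed LME effect of -2 kg.** At the 80% cut-off the ratio is -2/0.369 = -5.4 with the true proportion, -2/0.503 = -4.0 with k = 0.7 (error SD 10), and -2/0.648 = -3.1 with k = 0.5. At the 50% cut-off it is -2/0.821 = -2.4, against -2/0.941 = -2.1 and -2/0.991 = -2.0.

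**Step 5: other assumed distributions, half of misses reported.**
- Mean 65%, SD 22 points, noise giving r = 0.71: the share at or above 80% goes from 30.1% to 57.6% (shrinkage 1 - 30.1/57.6 = 48%), and at or above 50% from 74.3% to 97.8% (24%).
- Mean 75%, SD 20 points, no noise (r = 1.00): the share at or above 80% goes from 49.6% to 77.8% (36%).

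The direction is the same throughout. The size depends on the assumptions and is smaller at the lowest cut-off.

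**The case against.** **The reference is poor exactly when the rule applies.** The footnote comes into play only when the median return is below 50%. On the table's definition, a participant who brings back only some of the empty sachets is scored as less compliant than they were. The rule that fills a period from the other periods covers sachets that were not returned and does not mention partial returns. The count may then be biased, probably downward, which would inflate the CACE. Participants with no compliance data are treated as below 50%, so a measure with fewer gaps is a real gain. This stands. A reader might infer that switching to self-report is worse than keeping the count; the SAP does not show that.

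**Under-reporting is assumed.** A reader might infer that participants will over-report compliance. Nothing in the SAP shows this. The point is that the rule would not detect it.

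**The consequences are limited.** The switch is a contingency that may never apply. The CACE is supplementary, and the bias pulls it toward the intention-to-treat estimate and cannot create an effect. The figure of -5.4 kg above is not a true effect either: it assumes no effect in those just below 80% compliance (the exclusion restriction in 7.7.1). The illustration also leaves out the rule that scores zero sachets after discontinuation or loss to follow-up. All of this stands and limits the weight of the point.

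**The contrast with section 8.1 is only partial.** There the self-report concerns the primary outcome variable and is compared with a clinic measurement. It shows that the SAP knows the right tool, but it is not an internal contradiction.

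**The sign of the correlation.** Because the table counts used sachets and the footnote unused ones, a reader might infer that the sign is unclear. It is not: the footnote pairs unused with missed sachets, both count sachets not taken, and agreement gives a positive correlation.

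None of this makes a correlation a test of level.

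**Conclusion.** The point holds as a limited one. As written, 7.6 can replace the sachet count with self-report on the strength of a statistic that cannot see a proportional or constant shift, while compliance is used only at absolute levels. If 50-70% of misses are reported and true compliance averages 70% (both assumed), a self-report that passes the check overstates the proportion compliant enough to shrink the CACE by about 12-17% at the 50% cut-off and 26-43% at 80%. Whether this would happen is unknown, because the SAP gives no data on reporting and the switch needs all three conditions.

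The primary analysis is not affected. The SAP does not support calling the sachet count the truth, since incomplete returns may bias it in the other direction. The conclusion is that neither measure should be accepted or kept without an agreement check. The point is worth acting on because the repair is cheap.

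**What to change.** Amend the 7.6 footnote as follows:

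1. Express both measures as percent of expected sachets used.
2. In participant-periods with complete sachet returns, report the mean difference, the Bland-Altman limits of agreement, and agreement in complier classification at the cut-offs. State how many participants and periods contribute.
3. Do not let r >= 0.7 alone justify the switch. Base it on the results in item 2, judged while blinded to arm.
4. Whenever the low-return condition is met, report the compliance proportions and the CACE under both measures, and say that either may be biased.

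A fixed tolerance with automatic return to the count is not advisable, because it could reject accurate self-report when the count is too low.

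Cost: one revised footnote, a small extra table and two sets of supplementary results for the reader to weigh. No new data are needed, because the present rule already requires both measures.
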